5. RESEARCH ABSTRACT

Please provide a brief description in LAY language (understandable to an 8th grade student) of the aims of this project.

Clinicians who stigmatize people at risk of or living with HIV provide worse HIV testing, treatment, and linkage to care services to these populations. To date, the vast majority of stigma-reduction interventions for clinicians have occurred in single healthcare facilities. We propose to deliver evidence-based stigma reduction tools through a popular teletraining platform for clinicians, Project ECHO[®]. Project ECHO[®] (Extension for Community Healthcare Outcomes) has trained, supported, and empowered 70,000+ clinicians to provide a wide range of specialty care services in 37+ countries globally, including HIV testing, prevention, and linkage to care. It uses a "hub and spoke" model wherein non-specialists in community setting "spokes" learn from and collaborate with specialists at academic "hubs" via

videoconferencing technology (i.e., Zoom software). By delivering stigma-reduction tools through Project ECHO®, we could substantially extend the reach of stigma-reduction interventions for clinicians.

There are four phases of our project:

- **Phase 1:** We will explore experiences of stigma among people at risk of and living with HIV using Photovoice, a qualitative data collection technique involving photography and story-telling (n=35).
- **Phase 2:** We will explore clinicians' perspectives on an intervention to address stigma through online focus groups (n=40).
- **Phase 3:** We will conduct a brief pre-test of our intervention protocol with a small sample of clinicians (n=5).
- **Phase 4:** We will pilot test our intervention protocol among clinicians, comparing it to two control conditions (n=78). Our intervention materials will include Photovoice presentations created by participants in Phase 1 of the study. Importantly, these presentations will be screened to ensure that they do not contain identifying information (e.g., faces).

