Phase 4: *We will pilot test our intervention protocol with clinicians and compare it to two other intervention arms. Clinicians will be randomly assigned to one of three training conditions:*

1. *Participants randomized to the first control condition (n=26) will complete HIV Connect, which is an online course developed by the Malaysian Society of HIV Medicine designed to educate primary care physicians in Malaysia about HIV. It consists of a series of 9 modules and accompanying assessments featuring HIV infectious disease experts who instruct on topics including epidemiology and natural history of HIV, pre-exposure prophylaxis (PrEP) and post-exposure prophylaxis (PEP), sexual history taking and STI testing, and others. Participants will complete 1 module and assessment per month so that the intervention is delivered along the same timeline as the other two conditions (i.e., 9 months). The course is available free of charge to all registered medical practitioners in Malaysia. Clinicians earn Continuing Medical Education credits after completing each module and assessment, and a certificate of completion upon finishing all modules and assessments.*
2. *Participants randomized to the second control condition (n=26) will complete the standard version of Project ECHO for HIV Prevention, without added evidence-based stigma reduction tools. Participants will meet with the Project ECHO® Hub specialists and their learning community on a bi-weekly basis for 90 minutes over the course of 9 months. Their Hub specialists will include the infectious disease, mental/behavioral health, and family medicine specialists, but exclude the stigma expert and community representative. They will be joined periodically by guest*

speakers with expertise in infectious disease, pharmacology, case management, and other clinical topic areas. Each session will feature a didactic training incorporating standardized procedures for HIV testing, prevention, and/or linkage to care, and patient case presentation and discussion.

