3. *Participants randomized to our intervention (n=26) will complete Project ECHO® for HIV Prevention intervention with added evidence-based stigma reduction tools. Participants will meet with the Project ECHO® Hub specialists and their learning community on a bi-weekly basis for 90 minutes over the course of 9 months. Their Hub specialists will include the infectious disease, mental/behavioral health, and family medicine specialists, as well as the stigma expert and community representative. The stigma expert and community representative will monitor discussion and address stigmatizing content (e.g., via discussion and didactic training), thereby shaping social norms. The Hub specialists will be joined periodically by guest speakers with expertise in infectious disease, pharmacology, case management, and other clinical topic areas as well as stigma and key population communities. Each session will feature a didactic training, key population Photovoice presentation, and patient case presentation. In addition to addressing HIV testing, prevention, and linkage to care through the presentation of standardized procedures to facilitate education and behavioral design, didactic trainings will include content to increase education surrounding key populations. Weekly Photovoice presentations will facilitate extended contact with key populations and PLWH. Patient-case presentation and discussion will highlight at least one patient from a key population per week, facilitating clinical skills for and changing social norms surrounding working with key populations.*

All phase 4 participants will be invited to complete surveys. A subset of participants (up to 10 per condition) will be invited to participate in focus groups at the end of the intervention.

Citation: Wang, C. C. & Redwood-Jones, Y. A. (2001). Photovoice ethics: Perspectives from Flint photovoice. *Health Education & Behavior*, 28(5), 560-572.

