Phase 4: *Clinicians participating in the intervention pilot will benefit by receiving specialty training in HIV testing, prevention, and linkage to care. We believe that this will be desirable for some because some clinicians volunteer to receive this training via HIV Connect. Additionally, clinicians earn Continuing Medical Education credits after completing each module and assessment of HIV Connect, and a certificate of completion upon finishing all modules and assessments. We will seek approval for the Project ECHO arms to also be eligible for Continuing Medical Education credits, and will amend this protocol to reflect this benefit if our application is approved. Clinicians receive Continuing Medical Education credits for completing Project ECHO in the U.S. and elsewhere.*

Describe any potential future benefits to this class of participants, others, or society.

Clinician stigma remains a potent and persistent driver of disparities in HIV testing, prevention, and linkage to care globally. It is unlikely that we will eliminate these disparities and achieve equity in HIV testing, prevention, and linkage to care until we effectively address clinician stigma. The proposed project will result in important knowledge regarding the acceptability, feasibility, and preliminary impact of a significant and innovative strategy for reducing clinician stigma at large scale: the implementation of evidence-based stigma reduction tools via a popular teletraining platform. In light of the protections that we have in place within our study procedures, we believe that the risks to participants of this project are minimal. We therefore believe that the risks to participants are reasonable in relation to the importance of the knowledge that may be gained from this study.

If there is a Data Monitoring Committee (DMC) in place for this project, please describe when and how often it meets.

N/A

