Phase 4: *Quantitative analyses will be conducted in R version 3.6.2 and include an examination of descriptive statistics and generalized linear models. We will examine changes in mean self-reported stigma (i.e., prejudice, stereotypes, and discrimination) across the 3 time-points of data collection. We will use a two-way repeated measures ANOVA to determine whether any change in stigma is associated with the interaction between the type of condition (factor one) and time (factor two). Qualitative analyses will follow the same*

analytic steps and use the same software as those that we will apply Phases 1-3, except that our analysis will focus on interview transcripts. All qualitative focus groups will be transcribed by our trained research assistants. Results are expected to provide insight into the acceptability and feasibility of the intervention, including barriers to and facilitators of implementation and reasons for withdrawal, as well as participants' perceptions of impact on stigma and care delivery.

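### The only Phase 4 test given a purpose is the omnibus condition-by-time interaction; no contrast of ECHO plus stigma tools with standard ECHO is specified

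*Combined protocol and SAP*

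**What the plan says.** The quantitative plan for Phase 4 is one short paragraph in section 10 (DATA). It lists descriptive statistics and generalized linear models, with no outcome, predictor or contrast attached. It continues: "We will examine changes in mean self-reported stigma (i.e., prejudice, stereotypes, and discrimination) across the 3 time-points of data collection". It then names a two-way repeated measures ANOVA, whose purpose is to "determine whether any change in stigma is associated with the interaction between the type of condition (factor one) and time (factor two". No follow-up to a significant interaction, reference arm, main score or main survey is given.

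The intended comparison is described elsewhere. Section 5 says "We will pilot test our intervention protocol among clinicians, comparing it to two control conditions (n=78", and section 6 says the team will "pilot test our intervention protocol with clinicians and compare it to two other intervention arms". In section 6, the second control group "will complete the standard version of Project ECHO for HIV Prevention, without added evidence-based stigma reduction tools", while the intervention group receives Project ECHO "for HIV Prevention intervention with added evidence-based stigma reduction tools". Both ECHO arms meet with the "Hub specialists and their learning community on a bi-weekly basis for 90 minutes over the course of 9 months". The remaining control is the HIV Connect online course. Section 8 expects knowledge of acceptability, feasibility and the "preliminary impact of a significant and innovative strategy for reducing clinician stigma at large scale".

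**The concern.** The two ECHO arms share a format and a meeting schedule, and one of them adds the stigma-reduction components. The comparison directed at those components is therefore ECHO plus tools minus standard ECHO. The stated test does not make that comparison. It asks whether the three arms follow the same course over three surveys, and a significant answer names neither the arms that differ nor the direction.

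One pattern that would produce a significant result is that both forms of ECHO reduce stigma relative to HIV Connect and the tools add nothing. Another is that only the arm with the tools improves. These carry opposite messages about the tools, and the interaction p-value does not tell them apart. The stigma construct is described through three components measured at three surveys, so leaving the contrast, score and survey open also allows them to be chosen after the results are seen.

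**Working it through.** **Inputs from the protocol.** Three conditions of 26 (section 6), so 3 × 26 = 78, which matches section 5. Three time-points (section 10). No alpha, effect size, SD, within-person correlation or dropout rate is stated, so there is no power figure to reproduce.

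**Assumptions, not in the documents.** One baseline and two follow-ups with the full effect at both; SD 1; two-sided alpha 0.05; compound symmetry with correlation ρ = 0.3 / 0.5 / 0.7; complete data; no clustering.

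**1. Degrees of freedom.** Numerator (3 − 1)(3 − 1) = 4. Denominator (78 − 3)(3 − 1) = 150. The critical F is 2.43.

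**2. Noncentrality.** λ = 26 × (sum of squared interaction terms) / (1 − ρ). The effect on each cell is δ × (arm indicator) × (time indicator), so the sum is δ² × (centred sum of squares over arms) × (centred sum of squares over times).
- Times (0, 1, 1): 4/9 + 1/9 + 1/9 = 2/3.
- Both ECHO arms improve, arms (0, 1, 1): 2/3.
- Only the tools arm improves, arms (0, 0, 1): 1/9 + 1/9 + 4/9 = 2/3.

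At δ = 0.5 the sum is 0.25 × 2/3 × 2/3 = 0.111 in both patterns, and λ = 26 × 0.111 / (1 − ρ) = 4.13 / 5.78 / 9.63.

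**3. Rejection rates.**

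| Truth | Interaction, ρ = 0.3 / 0.5 / 0.7 | Direct contrast of the two ECHO arms |
|---|---|---|
| Both ECHO arms gain 0.5 SD, tools add nothing | 32% / 44% / 68% | about 5% |
| Only ECHO plus tools gains 0.5 SD | 32% / 44% / 68% | 66% / 71% / 84% |

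The direct contrast here is the baseline-adjusted mean of the two follow-ups (step 4). A simulation of 5,000 trials per setting gave 32 / 43 / 67% and 32 / 45 / 68% for the interaction. An unadjusted contrast of mean change rejected in 5.2 / 5.1 / 4.5% of trials in the first row.

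The equality between rows needs equal effects. If both ECHO arms gain only 0.25 SD, λ is a quarter as large and the interaction is significant 11% / 13% / 20% of the time.

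**4. Precision of the missing contrast.** In a three-arm model adjusted for baseline, the residual df are 78 − 3 − 1 = 74 and t = 1.993. SE = √(2/26 × V), where V is the variance left after adjustment.
- One follow-up: V = 1 − ρ² = 0.91 / 0.75 / 0.51; SE = 0.265 / 0.240 / 0.198; 95% half-width 0.53 / 0.48 / 0.39 SD.
- Mean of two follow-ups: V = (1 + ρ)/2 − ρ² = 0.56 / 0.50 / 0.36; SE = 0.208 / 0.196 / 0.166; half-width 0.41 / 0.39 / 0.33 SD.

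**5. Sensitivity to survey timing.** If the effect is 0.25 SD at the first follow-up and 0.5 SD at the second, the centred sum of squares over times is 0.125 and λ = 26 × (2/3) × 0.125 / (1 − ρ) = 3.10 / 4.33 / 7.22. Power falls to 24.4% / 33.5% / 54.0%, and remains the same in both patterns.

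**The case against.** The strongest reply is that the paragraph is not exhaustive. A generalized linear model with condition as a three-level factor would produce arm differences with standard errors, following up a significant interaction is common practice, and descriptive means by arm could show the pattern. This stands in part. A reader might infer that the plan omits the comparison with standard ECHO or rules out an estimate of it. The documents do not support that: sections 5 and 6 state the intention to compare, and the models that are named could deliver it. What is missing is the specification.

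A reader might also infer that subtracting standard ECHO from ECHO plus tools isolates the tools. That goes too far as well. Section 6 describes the added arm as a package: extra Hub members, additional guest speakers, Photovoice presentations and a regular key-population case. The protocol does not say how many learning communities each arm has. With one per arm, any difference between the arms is also a difference between two groups.

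Third, this is a pilot described on an IRB form, with acceptability and feasibility among its aims. Half-widths of 0.33 to 0.41 SD would not settle whether the tools work, and low power is not in itself an error here. That stands, and it is why the fix asks for an estimate with an interval rather than a powered test.

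Finally, the survey schedule is not described. Section 7 mentions a brief survey before assignment but does not say that it measures stigma, and section 15 lists updated measures among the uploads. Details of the instrument and timing may be there, so the figures above are an illustration only.

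**Conclusion.** The point holds as a gap in specification with an inexpensive remedy. The only Phase 4 test with a stated purpose cannot by itself answer whether adding stigma tools to ECHO makes a difference, and no contrast against either control is written. That conclusion follows from the 3 × 3 layout and needs no assumed numbers. The illustration shows its size: for equal 0.5 SD gains the interaction is exactly as likely to be significant when the tools add nothing as when they are the only thing that works. Those percentages depend on the assumed schedule, correlation and complete data. The point does not show that the trial is too small, nor that the named models could not supply the estimate. It should be fixed before the data are analysed.

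**What to change.** In section 10, keep the interaction test and add the following.

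- A pre-specified difference, ECHO plus tools minus standard ECHO, in one named stigma score, adjusted for the baseline score. Use the post-baseline surveys together, for example their mean, unless one survey is named for a stated reason. Report it as a pilot estimate with a 95% CI.
- The difference between ECHO plus tools and HIV Connect, reported the same way.
- A sentence describing the first difference as directed at the added stigma-reduction package as a whole.
- The number of learning communities in each ECHO arm. If each arm is a single community, state that the contrast also compares two groups and that its CI does not reflect group-level variation.

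This takes a few sentences and leaves sample size, surveys and conduct unchanged. The downside is that the team must commit in advance to a score and a main contrast.

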11. CONFIDENTIALITY

Will participants be audiotaped, photographed or videotaped during this study?

Phase 1: Participants will take photographs, however they will be instructed not to take photographs that include identifiable images (e.g., faces). Participants will not be audiotaped, photographed, or videotaped by the study team.

Phase 2: No audiotapes, photographs, or videotapes will be taken.

Phases 3-4: Participants will be audiotaped during their qualitative interviews and focus groups.

How will subject identity be protected?

Phase 1: We will ensure that photographs do not include identifying information. At the first Photovoice training, [name] will introduce techniques to protect participant identities (e.g., capturing people's shadows rather than faces). Participants will be instructed to not include identifying information in their photographs. Any photographs including identifying information will be destroyed and will not be included in final Photovoice presentations. All final Photovoice presentations will be screened to ensure that they include no identifying information. [name], [name], and [name] will choose the Photovoice presentations to be included in the intervention. They will then share these presentations with members of the study team, including Drs. [name], [name], and [name], who will screen the Photovoice presentations for identifying information. If any identifying information is found, the Photovoice presentations will be edited to ensure anonymity.

Phases 3-4: Audiotapes will be transcribed by a research assistant. During transcription, any references to participant identities will be removed. After transcription is complete, audiotapes will be deleted.

Is there a Certificate of Confidentiality in place for this project? (If so, please provide a copy).

As an NIH-funded study, it will automatically receive a Certificate of Confidentiality.

12. CONFLICT OF INTEREST

(For information on disclosure reporting see: <http://www.udel.edu/research/preparing/conflict.html>)

Do you have a current conflict of interest disclosure form on file through UD Web forms?

Yes

Does this project involve a potential conflict of interest*?

No

* As defined in the [University of Delaware's Policies and Procedures](#), a potential conflict of interest (COI) occurs when there is a divergence between an individual's private interests and his or her professional obligations, such that an independent observer might reasonably question whether the individual's professional judgment, commitment, actions, or decisions could be influenced by considerations of personal gain, financial or otherwise.

If yes, please describe the nature of the interest:

N/A

13. CONSENT and ASSENT

Consent forms will be used and are attached for review (see Consent Template under Forms and Templates in IRBNet)

Please note that we have submitted consent forms following the University of Malaya's consent templates.

Phases 2-4: *These studies will be conducted online and so we will not be able to collect signatures on study forms. We will include a signature box for participants to type in their name to document that they have read the information sheet and agree to continue with the study.*

Additionally, child assent forms will be used and are attached.

Waiver of Documentation of Consent (attach a consent script/information sheet with the signature block removed).

Please note that we have submitted consent forms following the University of Malaya's consent templates.

Phase 1: *The primary risk to participants is a breach of confidentiality. We therefore request a waiver of consent so that we do not have to keep records that include participants' names.*

Waiver of Consent (Justify request for waiver)

14. Other IRB Approval

Has this protocol been submitted to any other IRBs?

This protocol has been approved by the University of Malaya Medical Research Ethics Committee.

If so, please list along with protocol title, number, and expiration date.

Title: Implementing Stigma Reduction Tools via a Popular Teletraining Platform to Reduce

15. Supporting Documentation

Please list all additional documents uploaded to IRBNet in support of this application.

1. Progress report form
2. Protocol with and without tracked changes
3. Amendment form
4. Updated measures
 - 4.1.1 Focus group measures
5. Informed consent forms with and without tracked changes
 - 5.1.1 Including 2 consents for the 2 step consent process for Phase 4
6. Examples of de-identified PhotoVoice responses
7. Recruitment flyers for PhotoVoice study
8. Recruitment flyers for Project ECHO study
